2.5 Blinding

All participants, their clinical care team, their research nurse(s) response for follow-up, and all BTC staff will be unaware of the allocation order.

3. Populations

3.1 Study populations

3.1.1 Inclusion criteria

- Male aged ≥ 6 years old
- Clinical diagnosis of Barth syndrome with characteristic abnormality of the L4-cardiolipin/monolysocardiolipin ratio plus identified mutation in the tafazzin gene
 - Under the care of the NHS Barth Syndrome Service (BSS)
 - Stable cardiac condition
 - Able to swallow bezafibrate tablets (similar size to ibuprofen tablets)

3.1.2 Exclusion criteria

- Known hypersensitivity to bezafibrate, to any component of the product or to other fibrates
- Known photoallergic or phototoxic reactions to fibrates
- Hepatic dysfunction and/or liver function tests greater than 2x normal
- A shortening fraction of < 25 (or a significant drop in shortening fraction in the previous year)
- Documented atrial or ventricular arrhythmia (atrial/ventricular tachycardia or atrial/ventricular fibrillation) that has not been stabilised with treatment
- Renal impairment (creatinine clearance < 90 mL/min)
- Pre-existing known gallbladder disease
- Recent unspecified significant deterioration in general health
- Prisoners and adults lacking capacity to provide informed consent

3.2 Data sources

All study data will be collected on case report forms (CRFs), with the exception of the mitochondrial data required to answer the MLCL/L4-CL ratio / cardiolipin profile outcomes, the MRS data required to answer PCr/ATP ratio and skeletal muscle oxidative function outcomes, the MRI data required to answer the MRI cardiac function outcomes, and the mitochondrial data. These data will be obtained and recorded in spreadsheets by the laboratory staff, sent to the study statistician, and linked using studyid.

3.3 Analysis populations

3.3.1 Intention-to-treat population

All summaries and analyses of the primary and secondary outcomes will be conducted on the intention-to-treat (ITT) population. The ITT population will consist of all participants and periods, included according to the sequence they were randomised to and the treatment they were randomised in that given period, regardless of whether they are ineligible, prematurely discontinued treatment or are otherwise protocol violators/deviators.

3.3.2 Per-protocol population

In addition to the ITT analysis, a complier average casual effect (CACE) analysis will be considered for the primary outcome if there are a considerable number of major protocol deviators ($> 20\%$ of participants). The number of protocol deviators and the extent of the protocol deviations will be monitored.

Major protocol deviators include the following:

- Incorrect unblinding procedure
- Any serious breaches to the protocol, defined as those events that affect the confidentiality or safety of participants, or the integrity of the trial
- Participant does not meet the study eligibility criteria, but receives a single dose of study treatment

In order to assess the utility of a per-protocol analysis, the proportion of protocol deviators will be assessed, without reference to outcome data, through a blinded examination of the population at the time of analysis by the study statistician in co-operation with other members of the TMG.

3.3.3 Safety population

The safety population will consist of all randomised participants, included according to the treatment they actually received in each treatment period, and who have received at least one dose of trial treatment.

3.4 Withdrawals

Participants can withdraw/be withdrawn from treatment and/or follow-up at any stage of the trial at their own discretion or that of the treating clinician. All participants withdrawn from the trial, in addition to those found to be ineligible post-randomisation, will be continued to be followed up until the end of the study, unless they withdraw full consent for further follow-up data to be collected. All data previously collected by the participant will be used in the analysis, unless they have withdrawn full consent from collected data to be used.

4. Statistical analyses and report content

4.1 General considerations

Statistical analysis is the responsibility of the BTC study statistician and all analyses will be carried out using the most recent version of the statistical software at the time of analysis.

Where treatments are being compared formally using statistical modelling, the placebo group will act as the reference category, in order for interpretations to be in the form: the effect of bezafibrate in comparison with placebo. All applicable statistical tests will be 2-sided and will be performed using a 5% significance level, with the exception of tests for interactions that will be performed using a 10% significance level, and confidence interval will be 95% unless otherwise stated.

No formal adjustment will be made for multiple testing, but consideration will be taken in interpretation of results to reflect the number of statistical tests performed and the consistency, magnitude and direction of treatment estimates for different outcomes.

4.2 General calculations

Unless otherwise stated, all percentages will be calculated using the total number of participants with data available for that variable, with any missing data mentioned in footnotes. For categorical and binary data, all percentages will be rounded to at most 1 decimal place, and for continuous measures, these will be summarised to one more decimal place than the data is collected. P-values >0.001 will be summarised to 2 significant figures, and those <0.001 will be reported as <0.001).

4.3 Outcomes

4.3.1 Primary outcome

- Peak VO₂

4.3.2 Secondary outcomes

Secondary outcome measures include:

- MLCL/L4-CL ratio / cardiolipin profile
- PCr/ATP ratio
- Skeletal muscle oxidative function
- Quality of life
- Absolute neutrophil count
- Amino acid expression
- Cardiac function
- Lymphocyte mitochondria
- Arrhythmia profile

4.4 Definition and derivation of the outcomes

4.4.1 Primary outcome

Peak VO₂ is defined as the peak oxygen consumption on bicycle ergometry at baseline and in the final week of each treatment period.

4.4.2 Secondary outcomes

MLCL/L4-CL ratio / cardiolipin profile

Participants will be assessed for their monolysocardiolipin/tetralinoleoyl-cardiolipin (MLCL/L4-CL) ratio calculated using results from mitochondrial assessments carried out at baseline and in the final week of each treatment period.

PCr/ATP ratio

Participants will be assessed for their phosphocreatine/adenosine triphosphate (PCr/ATP) ratio, assessed via myocardium and oxidative function using a ³¹P magnetic resonance spectroscopy (MRS). These assessments will only be carried out in the final week of the second treatment period due to delays in approving the technology.

Skeletal muscle oxidative function

Participants will be assessed for their skeletal muscle oxidative function using a ³¹P MRS in the final week of the second treatment period.

Quality of life

Quality of life (QoL) will be assessed using age-appropriate PedsQL questionnaires at baseline and in the final week of each treatment period. The PedsQL will be scored according to guidelines set out in the PedsQL user [1].

Absolute neutrophil count

Neutrophil count will be gained from blood tests at baseline and as part of the monthly blood tests taken throughout both treatment periods.

Amino acid expression

Amino acid expression will be derived from participants' arginine and cysteine levels, and will be assessed at baseline and as part of the monthly blood tests throughout both treatment periods.

Cardiac function

Participants' cardiac function will be assessed using echocardiogram, at rest and during exercise, at baseline and in the final week of each treatment period.

Lymphocyte mitochondria

Participants' lymphocyte mitochondria will be assessed by electron microscopy, at baseline and in the final week of each treatment period.

Arrhythmia profile

Participants' arrhythmia profile will be assessed using 12-lead electrocardiogram (ECG), at rest and during exercise, at baseline and in the final week of each treatment period.

4.5 Analysis of the outcomes

4.5.1 Primary outcome

Peak VO₂

Peak VO₂ (VO₂ max (ml/kg/min)) will be the primary analysis, and will be analysed formally using a mixed linear regression model to compare bezafibrate against placebo, adjusting for period as a fixed effect (exploring interactions where necessary) and participants as random effects. Nested models will be compared using the likelihood ratio test. Model assumptions will be tested using standard methods, including residual plots etc., and a test for carry-over will be carried out by including treatment sequence in the model. If these assumptions do not appear to be valid then alternative methods will be explored.

Rest VO₂ will also be analysed formally in a similar way to peak VO₂. Peak wattage achieved (when peak VO₂ is measured) will be assessed for consistency within participants across time periods by calculating the correlation.

Peak and rest VO₂, and 2 and 6 min recovery VO₂ will also be summarised descriptively using means and standard deviations (SDs) (or medians and interquartile ranges (IQRs) depending on the distribution) at each period separately, and graphical representations of the distribution will be presented by treatment and period.

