2.4 Sample size

This is a single centre study to be performed in patients attending the NHS National Barth Syndrome Service. A total of 18 males aged between six and 24 years currently attend the service. We anticipate that between 12 and 15 UK patients are likely to consent to take part.

In a simple crossover trial (a single intervention and control comparison), the standard deviation (SD) of the within subject difference between treatments is given as: square root of 2 times the within subject SD. In a crossover trial, all participants act as their own control.

In this trial, the difference in mean peak volume of O₂ consumption between placebo and bezafibrate phases will be tested, assuming a 2-tailed type I error of 5%. For a sample size of 12 participants, the trial will be able to detect a difference of 0.90 (within subject) SDs with 80% power, or 1.05 SDs with 90% power.

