4.5.2 Secondary outcomes

MLCL/L4-CL ratio / cardiolipin profile

MLCL/L4-CL ratio will be analysed formally using a mixed linear regression model to compare bezafibrate against placebo, in the same way, using the same methods as the primary analysis of peak VO₂ above.

MLCL/L4-CL ratios will also be summarised descriptively using means and SDs (or medians and IQRs) by treatment and period, and graphical representations of the distributions will be presented by treatment and period.

Cardiolipin profile will be analysed visually by the laboratory team and will not form part of the statistical analysis.

PCr/ATP ratio

PCr/ATP ratio for the second period will be summarised descriptively using a mean and SD (or median and IQR) by treatment and overall, and graphical representations of the distribution will be presented by treatment and overall.

Skeletal muscle oxidative function

Skeletal muscle oxidative function (a panel of quantities to determine function) for the second period will be summarised descriptively using means and SDs (or medians and IQRs) by treatment and overall, and graphical representations of the distribution will be presented by treatment and overall.

Quality of life

Quality of life (QoL) index score, derived from value sets calculated via the responses for each domain of the PedsQL questionnaire, will be analysed formally using a mixed linear regression model to compare bezafibrate against placebo, in the same way, using the same methods as the primary analysis of peak VO_2 above, for participants of each age group and parents/carers separately.

Participants' and parents'/carers' QoL scores for each domain of the questionnaire will also be summarised descriptively using means and SDs (or medians and IQRs) or counts and percentages (where appropriate) by treatment and period, and graphical representations of the distributions will be presented by treatment and period.

Absolute neutrophil count

Absolute neutrophil count will also be analysed formally using a mixed linear regression model to compare bezafibrate against placebo, in the same way, using the same methods as the primary analysis of peak VO_2 ratio above.

Amino acid expression

Plasma arginine and plasma cysteine values will also be analysed formally using mixed linear regression models to compare bezafibrate against placebo, in the same way, using the same methods as the primary analysis of peak VO_2 ratio above.

Cardiac function

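### The SAP names only a large-sample likelihood ratio test for a mixed model on 12 to 15 participants; if that tests the treatment effect, a nominal 5% test runs at about 7 to 8%

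*SAP*

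**What the plan says.** - **Primary model (SAP 4.5.1).** Peak VO₂ is compared between bezafibrate and placebo in a linear mixed model, with period as a fixed effect and participant as a random effect. Interactions may be explored. The next sentence is "Nested models will be compared using the likelihood ratio test". Neither this section nor any other mentions ML or REML, a t or F reference, degrees of freedom or a small-sample correction. Alternative methods come in only if the model assumptions look invalid.
- **Error rate (SAP 4.1).** "All applicable statistical tests will be 2-sided and will be performed using a 5% significance level", with 10% for interaction tests and 95% confidence intervals. How the intervals are built is not stated.
- **Size (SAP 2.4).** "We anticipate that between 12 and 15 UK patients are likely to consent to take part"; 18 males attend the service. The power statement is "For a sample size of 12 participants, the trial will be able to detect a difference of 0.90 (within subject) SDs with 80% power". For 90% power, the detectable difference given is 1.05 SDs.
- **Reach (SAP 4.5.2).** The MLCL/L4-CL ratio, quality of life, neutrophil count, arginine, cysteine and the main echo and MRI parameters are to be analysed "using the same methods as the primary analysis".

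**The concern.** The chi-square reference for a likelihood ratio statistic is a large-sample approximation. In a complete two-period crossover the treatment effect rests on one within-participant difference per person, with n − 2 degrees of freedom for its variance: 10 at n = 12. At that size the approximation rejects too often under the null. Residual plots would not show this, because the model can fit well while the reference distribution is wrong, so the fallback in 4.5.1 would not be triggered.

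At stake is whether the primary test keeps the 5% level that the SAP promises. The error favours declaring an effect, and it would decide the result when the p-value lies near 0.05. Section 4.1 makes no formal multiplicity adjustment, so nothing later absorbs the excess.

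**Working it through.** **Inputs.** n = 12 (basis of the sample size), 15 (upper end of expected consent) and 18 (all who attend the service), from SAP 2.4; two-sided 5% and 95% intervals, from 4.1; the model, from 4.5.1. Assumptions: complete data, normal errors, equal or near-equal sequences, and only the two end-of-period values as responses.

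**1. The SAP's own power figures.** Power = P(|T| > t₀.₉₇₅,df), with T noncentral t and noncentrality d√n, where d is the difference in SDs of the within-participant difference. With n = 12:

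| d | Stated power | t, 11 df | t, 10 df | Normal reference |
|---|---|---|---|---|
| 0.90 | 80% | 81.0% | 80.2% | 87.7% |
| 1.05 | 90% | 91.1% | 90.5% | 95.3% |

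The stated figures reproduce with a t reference and not with a normal one. This requires reading SD as the SD of the difference, which 2.4 gives as "square root of 2 times the within subject SD". If SD is read as the within-subject SD, as labelled, power is about 52% and 65% (t, 11 df). That labelling is a separate matter.

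**2. Size of the likelihood ratio test.** For complete two-period data the ML statistic for treatment is

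LRT = n · ln(1 + t²/(n − 2)), with t on n − 2 df under the null.

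Rejecting when LRT > 3.841 means rejecting when t² > (n − 2)(exp(3.841/n) − 1). At n = 12: 10 × (1.3773 − 1) = 3.773, so |t| > 1.942, where the exact critical value is 2.228.

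| n | Rejects at \|t\| > | Exact critical value | True size |
|---|---|---|---|
| 12 | 1.942 | 2.228 | 8.1% |
| 15 | 1.948 | 2.160 | 7.3% |
| 18 | 1.951 | 2.120 | 6.9% |

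Simulation of the ML fit with the participant variance held non-negative (100,000 replicates per setting, n = 12) gave 8.0 to 8.3% for within-participant correlations of 0.3 to 0.9, and 9.3% at correlation 0.

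**3. A Wald z test instead, n = 12.**
- REML standard error: P(|t₁₀| > 1.960) = 7.8%.
- ML standard error, smaller by √(10/12): P(|t₁₀| > 1.960 × 0.913) = P(|t₁₀| > 1.789) = 10.4%.

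**4. Intervals, if normal-based, n = 12.** Width relative to the exact t interval:
- REML: 1.960/2.228 = 0.88, so 12% too narrow, with coverage of about 92.2%.
- ML: 1.789/2.228 = 0.80, so 20% too narrow, with coverage of about 89.6%.

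**5. With a t reference.** Referring the estimate to t on 10 df gives 5% by construction; the simulated size at n = 12 was 4.8 to 5.0%.

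**The case against.** The strongest reply is that the SAP never says that the treatment p-value comes from the likelihood ratio test. The sentence follows the mention of interactions and precedes the carry-over test, so it may concern only which terms stay in the model, with treatment tested from its fitted coefficient. That reading is open. A reader might infer that the primary test is fixed at 8%; the text does not support so firm a statement. What stands is that no other test is named. A coefficient test with a z reference is oversized too, and only an unstated t reference gives 5%.

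A reader might also infer that the planned intervals are too narrow. The SAP gives only their level and names no software whose default could be assumed, so the 12% and 20% figures are conditional.

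The 8.1% depends on the data layout. Section 4.4.1 defines peak VO₂ at baseline as well as at the end of each period. If baseline entered as a third response, with complete data and compound symmetry, within-participant df would be 2n − 3 = 21 at n = 12 and the size about 7.0% (6.5% at n = 15): smaller, but still above 5%.

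Nor does the figure carry over unchanged to every secondary outcome. Neutrophils, arginine and cysteine are measured monthly, and quality of life is modelled separately by age group. The age-group models have fewer participants, so the small-sample error there would be larger.

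Finally, the excess is about 2 to 3 percentage points over the expected recruitment range, and 4.1 promises cautious interpretation across outcomes. That limits the practical effect but does not restore the stated error rate.

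**Conclusion.** The point holds in conditional form. The SAP leaves the reference distribution for its primary treatment test open, and the one test that it names is a large-sample test. Used for the treatment effect, that test has a true size of about 8.1% at n = 12 and 7.3% at n = 15, and 6.9% even if all 18 patients took part. These figures assume complete data and the two end-of-period responses.

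The mismatch with the design does not depend on how the likelihood ratio sentence is read. The sample size figures embody a t reference that the analysis section does not carry over. The documents do not establish that the primary test will run at 8%, that the intervals will be normal-based, or that all secondary outcomes share the same inflation.

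**What to change.** In SAP 4.5.1, state that the mixed models are fitted by REML, and that the treatment p-value and 95% confidence interval come from a t reference with Kenward-Roger (or Satterthwaite) degrees of freedom. State that the chi-square likelihood ratio test is not used for the treatment effect. If it is kept for any other purpose, say which. Apply the same wording to all outcomes in 4.5.2 that follow the primary method, including the monthly blood measures and the age-group quality of life models. Say also whether the baseline value is a response in the model, since this changes the degrees of freedom.

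For complete data with two responses per participant, this gives the same answer as a two-sample t-test on period differences with n − 2 df.

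The cost is a sentence or two of text and a software option. P-values become slightly larger and intervals wider; at n = 12 the multiplier is 2.228 in place of 1.960. No planned power is lost, because the stated power already rests on a t reference.

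### SAP section 4.5.1 does not protect the crossover estimate as the primary result: low-power tests on the trial data may change the model, with no stated limit

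*SAP*

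**What the plan says.** Section 4.5.1 fits a mixed linear model for peak VO₂ comparing bezafibrate with placebo, "adjusting for period as a fixed effect (exploring interactions where necessary"), with participants as random effects. It then has nested models compared by likelihood ratio test, calls for residual checks, and adds that "a test for carry-over will be carried out by including treatment sequence in the model". The next sentence reads "If these assumptions do not appear to be valid then alternative methods will be explored".

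Section 4.1 makes placebo the reference category and sets tests at two-sided 5%, "with the exception of tests for interactions that will be performed using a 10% significance level".

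The SAP does not give the level of the carry-over test, what follows a positive result, which interactions may be kept, or what the alternatives are. It does not say that the base model remains the primary result. Section 4.5.2 applies the same methods to the formally analysed secondary outcomes: MLCL/L4-CL ratio, quality of life, neutrophil count, arginine and cysteine, and the main echocardiographic and MRI parameters.

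**The concern.** The trial gets its precision from comparing each participant with himself. Section 4.5.1 lets tests on the same small data set decide whether that comparison is kept. The sentence on alternatives follows directly on the carry-over test, so its natural reading counts absence of carry-over among the assumptions whose failure triggers a change.

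Two things are at stake. First, the sequence contrast compares 6 participants with 6 others, so it has little power for real carry-over. It is also strongly correlated with the first-period comparison, a common replacement when carry-over is suspected. Second, a retained treatment-by-period term changes what the bezafibrate coefficient estimates, whatever the alternative methods turn out to be.

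**Working it through.** **Inputs.** From the SAP: 12 participants, two-sided 5%, detectable differences of "0.90 (within subject) SDs with 80% power, or 1.05 SDs with 90% power", and SD of the treatment difference equal to "square root of 2 times the within subject SD" (section 2.4); 1:1 sequences (2.2); 10% for interaction tests (4.1). Assumed, because the SAP does not give them: exactly 6 per sequence, complete data, and a within-participant correlation ρ of peak VO₂ from 0.3 to 0.9. The within-subject SD is set to 1, so the between-participant variance is ρ/(1−ρ).

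**1. The stated power.** Take 0.90 as a multiple of the SD of the within-participant difference. The noncentrality is 0.90 × √12 = 3.12, and power is 81.0% (11 df) or 80.2% (10 df, period-adjusted). For 1.05 it is 91.1% or 90.5%. The plan's figures are reproduced on this reading. Read literally as within-subject SDs, the noncentrality is 0.90 × √6 = 2.20 and power is only 52%. That labelling question is separate. Here the design effect is taken as 0.90 × √2 = 1.27 within-subject SDs.

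**2. Sequence and treatment-by-period are one contrast.** The design has four sequence-by-period cell means. Intercept, treatment, period, sequence and treatment-by-period make five columns of rank 4, so the last two cannot be separated.

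**3. What each term does to the treatment estimate.** In one simulated balanced data set, the base model gave 0.850 (SE 0.328). Adding sequence left both figures unchanged. Adding treatment-by-period instead, with placebo and period 1 as references, gave −0.937 (SE 1.691), which is the period-1 difference between the two groups. In general:
- crossover SE = √(1/6) = 0.41
- period-1 SE = √(1/[3(1−ρ)])
- ratio = √(2/(1−ρ)), which is 1.7 at ρ = 0.3, 2.6 at 0.7 and 4.5 at 0.9.

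**4. Power of the carry-over test.** The test compares participant sums between sequences, with SE = √(2(1+ρ)/[3(1−ρ)]) and 10 df. For carry-over equal to the design effect, the noncentrality is 1.27/SE:

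| ρ | SE | Power at 10% |
|---|---|---|
| 0.3 | 1.11 | 28.5% |
| 0.5 | 1.41 | 21.7% |
| 0.7 | 1.94 | 16.3% |
| 0.9 | 3.56 | 11.9% |

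For carry-over of half that size at ρ = 0.8, power is 11%.

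**5. Type I error if a positive test leads to a period-1 analysis.** The correlation between the sequence contrast and the period-1 contrast is √((1+ρ)/2), from 0.81 (ρ = 0.3) to 0.97 (ρ = 0.9). Simulation with 200,000 trials per setting, no treatment effect and no carry-over:

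| ρ | Overall, 5% pre-test | Overall, 10% pre-test | Period-1 test rejects after a positive 10% pre-test |
|---|---|---|---|
| 0.3 | 6.8% | 7.5% | 30% |
| 0.5 | 7.2% | 8.1% | 36% |
| 0.7 | 7.9% | 8.6% | 41% |
| 0.8 | 8.1% | 9.0% | 44% |
| 0.9 | 8.6% | 9.4% | 48% |

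Repeat runs differ by 0.1 to 0.2 points. Check at ρ = 0.9 with a 10% pre-test: 0.10 × 0.48 + 0.90 × 0.05 = 0.093. Without switching, type I error is 5.0%. At the design effect, switching after a 10% pre-test gives power of about 77%, against 80% without it. A period-1 analysis alone has 39% (ρ = 0.3) down to 10% (ρ = 0.9).

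**6. The likelihood ratio test.** For this contrast the statistic is n·log(1 + t²/(n−2)). With n = 12, the chi-square cut-off 3.84 corresponds to |t| = 1.94 on 10 df, an actual size of 8.1% at nominal 5%. The cut-off 2.71 corresponds to |t| = 1.59, an actual size of 14.3% at nominal 10%. Selection by this test therefore fires falsely more often than its nominal level.

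**The case against.** A reader might infer that the SAP prescribes the classical two-stage crossover procedure, and so that its primary test runs at about 9%. The text does not support that:

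- No section names a first-period analysis as the replacement. Another alternative would give another error rate, and if nothing is switched the rate is 5%.
- The assumptions in question may be mainly those checked by residual plots. The natural reading includes carry-over, but the sentence is ambiguous.
- The sequence term does no harm by itself: with complete, balanced data the treatment estimate and its SE do not move. Harm needs a switch of method or a retained treatment-by-period term.
- The 10% level is stated only for interactions. Carry-over is to be tested through a sequence main effect, for which 5% is the literal default. The 10% figures apply if the same contrast is tested as an interaction.
- The SAP gives no correlation, and section 2.4 expects 12 to 15 participants, so 6 per sequence is an assumption.

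It would also go too far to say that the test protects against nothing. Its power is poor, but not zero.

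All of this stands, and it limits the size of the point. It does not remove it: the text still lets the data choose the primary model, and a method chosen afterwards from an unnamed set has no error rate that can be stated in advance.

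**Conclusion.** The concern holds as a defect in what section 4.5.1 fixes. The SAP permits a two-stage analysis without prescribing one, and no sentence keeps the crossover estimate primary. The aliasing in step 2 and the change of meaning in step 3 follow from the design and from ordinary reference coding, and need no assumption about the alternative methods.

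The error rates are conditional. Type I error is 5% with no switching. With a first-period fallback, 6 per sequence and ρ from 0.3 to 0.9, it is about 6.7–8.6% (5% pre-test) or 7.4–9.4% (10% pre-test). The direction is the same over the whole range of ρ; the exact figure is not known. The SAP should be changed before analysis.

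**What to change.** In section 4.5.1:

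1. State that the model with treatment, period and random participant gives the primary result whatever the sequence or interaction terms show.
2. Report the sequence (equivalently treatment-by-period) estimate with its 95% CI as descriptive or sensitivity information only. Rest the absence of carry-over on the one-month washout in section 2.1.
3. Remove likelihood-ratio selection of a treatment-by-period term from the primary model.
4. Limit alternative methods to distributional problems and name one fallback in advance, for example a rank test on the period differences by sequence. Other choices would serve, provided one is fixed.

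Because section 4.5.2 refers back to this text, the same edit repairs the formally analysed secondary outcomes.

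The cost is SAP wording and the loss of a low-power carry-over test as a trigger. The sequence estimate is still reported, and neither the data collected nor the sample size changes.
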